2.4.2 Prior, concomitant and post therapies

Prior and concomitant medications will be summarized in separate tables by treatment group.

Concomitant rescue and other anti-malarial medications will also be summarized by treatment group.

Note – rescue medications and non-study antimalarial drugs are the same. If they are used after discontinuation of study drug due to early treatment failure, late clinical failure or late parasitological failure then they should be considered as rescue medications, otherwise, they are considered as other non-study drug antimalarial medications. Rescue medications will be captured along with other concomitant medications by the investigators under rescue medication category.

Prior medications are defined as drugs taken and stopped prior to first dose of study medication. Any medication given at least once between the day of first dose of study medication and the last day of study visit will be a concomitant medication, including those which were started pre-baseline and continued into the treatment period.

Prior and concomitant medications will be coded according to the latest version of WHO Drug Reference List dictionary which employs the ATC. The number and percentage of patients taking prior and concomitant medications will be summarized for each treatment by ATC class and preferred term (PT).

Number and percentages of the patients received prohibited prior and concomitant drugs will be summarized

Safety set will be used.

2.5 Analysis of the primary objective

The PK Run-in Part will be separately analyzed. The primary objective for the part is to investigate the pharmacokinetic interaction potential between KAF156 and LUM-SDF. The analyses of PK parameters of KAF156 and LUM-SDF are detailed in [Section 2.9](#).

The primary efficacy objective in Part A is to determine the effective dose of KAF156 combined with LUM-SDF given daily over 1, 2, 3 days for treatment of uncomplicated malaria caused by *P. falciparum* in adults/adolescents. If there are multiple KAF156 and LUM-SDF dose combinations that are effective, tolerable and safe, the most effective dose combination(s) in the less frequent 1 to 2 days regimen and the most effective dose combination(s) in the 3 days regimen will be carried over to Part B. Up to 3 KAF156 and LUM-SDF dose combinations may be carried over to Part B.

The primary efficacy objective in Part B is to determine if the selected dose combination regimens (adjusted for body weight) from Part A are effective in children down to 2 years.

2.5.1 Primary endpoint

The primary efficacy variable is the PCR corrected Adequate Clinical and Parasitological Response (ACPR) at Day 29 (see [Section 2.1](#)).

2.5.2 Statistical hypothesis, model, and method of analysis

The statistical null hypothesis is that the ACPR rate at Day 29 is at most 80% with the alternative hypothesis that the ACPR rate at Day 29 is greater than 80%. The statistical hypothesis will be evaluated using the lower limit of 2-sided 95% exact confidence interval (CI) (Pearson-Clopper method) for the ACPR rate at Day 29. If the lower limit of 2-sided 95% exact confidence interval for the ACPR rate at Day 29 is greater than 80%, the null hypothesis will be rejected. The statistical hypothesis testing will be evaluated separately for each KAF156 and LUM-SDF combination in each part based on the PPS. There is no adjustment for multiplicity since this is an exploratory study.

2.5.3 Handling of missing values/censoring/discontinuations for primary endpoint analysis

Parasite assessments obtained within the protocol specified visit window for Day 29 (Day 25 to Day 33) will be considered as the assessment for Day 29.

No missing data are expected for the primary efficacy analysis based on PPS since patients who are not evaluable for the primary efficacy variable are excluded from PPS. See [Section 2.5.4](#) for missing data handling for the supportive analysis using FAS.

2.5.4 Supportive analyses

The primary efficacy variable will be performed based on the FAS using the statistical method specified in [Section 2.5.2](#).

Primary efficacy variable will be handled additionally for those patients who are excluded from the PPS as follows:

- Presence of parasitemia which cannot be determined to be recrudescence or reinfection due to missing PCR data will be counted as non-responders (from the day of test)
- Missing/underdetermined responses at Day 29 due to missing blood smear data at the visit will be counted as non-responders unless there is a later blood smear test indicating no parasitemia
- Patients who received non-rescue anti-malarial medication will be considered in the analysis as if they had not taken the anti-malarial drug.
 - Note: These patients did not experience any treatment failure (ETF, LFT, or LPF). In case that non-PPS patients who experienced treatment failure, they will be included as non-responders if they received rescue medication for the treatment of *P. falciparum* malaria due to recrudescence or as responder for PCR corrected ACPR if they received rescue medication for treatment of a new infection on Day 8 or later.

For exploratory purpose, 2-sided 95% confidence intervals for the difference in ACPR at Day 29 between each KAF156/LUM-SDF treatment group and Coartem[®] will be constructed using the Wilson uncorrected method.

Let

a = # patients with responders in investigational arm

c = # non-responders in investigational arm

m = sample size of investigational arm ($a+c$)

b = # responder in control arm

d = # in control arm

n = sample size of control arm ($b+d$)

$\theta = \pi_1 - \pi_2$ is the treatment difference

$\hat{\theta} = a/m - b/n$ is estimated treatment difference

Method based on the Wilson score method for the single proportion, without continuity correction:

$L = \hat{\theta} - \delta$, $U = \hat{\theta} + \varepsilon$ where

$$\delta = \sqrt{\{(a/m - l_1)^2 + (u_2 - b/n)^2\}} = z\sqrt{\{l_1(1 - l_1)/m + u_2(1 - u_2)/n\}}$$

$$\varepsilon = \sqrt{\{(u_1 - a/m)^2 + (b/n - l_2)^2\}} = z\sqrt{\{u_1(1 - u_1)/m + l_2(1 - l_2)/n\}}$$

l_1 and u_1 are the roots of $|\pi_1 - a/m| = z\sqrt{\{\pi_1(1 - \pi_1)/m\}}$, and l_2 and u_2 are the roots of $|\pi_2 - b/n| = z\sqrt{\{\pi_2(1 - \pi_2)/n\}}$.

where z is the standard normal deviate associated with 5% level of significance (l.o.s.) two sided.

In planned analysis of PCR corrected ACPR at Day 29, PCR corrected ACPR rate at Day 29 was to be calculated by considering patients with new infections prior to Day 29 as PCR corrected ACPR. In order to assess the impact of new infections on the PCR corrected ACPR rate, two sensitivity analysis will be performed. In the first analysis, PCR corrected ACPR rate will be recalculated by excluding the patients with new infections occurring prior to Day 27. It is seen that new infections were reported more on Day 29 visit compared to prior to Day 29 visit. In another sensitivity analysis, patients with new infections occurring up to Day 29 will be excluded and PCR corrected ACPR rate will be recalculated in the remaining patients. Analyses will be based on Per-protocol set for PK Run-in, Part A and B.

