### **5.6.6 Rescue medication**

The following circumstances warrant discontinuation of study treatment and the implementation of rescue medication (see [Section 6.5.8](#)):

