#### 9.4.4 Sensitivity analyses

The primary efficacy variable will be performed based on the FAS using the statistical method specified in [Section 9.4.2](#). Missing primary efficacy variable will be handled as follows:

- Patients who received rescue medication for the treatment of *P. falciparum* malaria (except for the treatment of a new infection) will be considered treatment failures (from the day of rescue use onwards).
- Patients who received other concomitant medication having an effect on malaria for reasons other than rescue therapy e.g. for the treatment of *P. vivax* or for the treatment of *P. falciparum* gametocytes (e.g., primaquine, certain antibiotics (sulfonamides, tetracycline, etc.)) will be considered in the analysis as if they had not taken the drug.
- Patients will be counted as failure if (a) they did not have a parasite count at Day 29 unless these patients could be classified as cured based on absence of parasitemia at later time, or (b) they did not have valid PCR evaluations at baseline and Day 29 if parasitemia was present at Day 29.

In addition, for the FAS, the proportion of patients with PCR-corrected ACPR at Day 29 and 95% CI will be also estimated using the Kaplan-Meier method ([Stepniewska and White 2006](#) and [WHO 2015](#)) which uses treatment failure as the event and treats missing data as censored instead of treatment failure. The PCR-corrected ACPR rate at Day 29 is estimated by the survival function at Day 29. Patients who had a new infection (i.e., reinfection) with *P. falciparum* or other species without *P. falciparum* recrudescence on or after Day 8 will be censored at the time of the first PCR that indicate the infection; patients who took antimalarial

medications for reinfection or reasons other than rescue medication given for signs and symptoms of infection with *P. falciparum* or unsatisfactory therapeutic effect will be censored at the first time of such antimalarial medications; other patients without treatment failure will be censored at the time of last parasitemia assessment.

A two-sided 95% CI for the difference in proportion between each KAF156/LUM-SDF combination treatment group and Coartem® will be calculated based on the variance of individual proportion using the Greenwood formula.

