#### 9.5.1.1 PCR-corrected ACPR and uncorrected ACPR

At each visit, the mean ACPR rate with 95% confidence intervals will be provided using Pearson-Clopper method for each treatment group.

Data will be handled as follows:

- Treatment failures after 7 days (i.e., Day 8) due to reinfection based on PCR genotyping are not considered as failure for PCR-corrected analyses.
- For parasitological uncorrected ACPR, patients will be treated as failure on and after the visit when a new infection (i.e., reinfection) with *P. falciparum* or other species is detected.
- Patients who received rescue medication for the treatment of *P. falciparum* malaria (except for the treatment of a new infection) will be considered treatment failures (from the day of rescue use onwards). Patients who received other concomitant medication having an effect on malaria for reasons other than rescue therapy e.g. for the treatment of *P. vivax* or for the treatment of *P. falciparum* gametocytes (e.g. primaquine, certain

antibiotics (sulfonamides, tetracycline, etc.) will be considered in the analysis as if they had not taken the drug.

- Patients will be counted as failure at a visit (e.g., Day 15, etc.) if (a) they did not have a parasite count at that visit unless these patients could be classified as cured based on absence of parasitaemia at a later time (e.g., Day 29), or (b) they did not have valid PCR evaluations at baseline and the visit if parasitaemia was present at that time (e.g., Visit Day 15).

In addition, PCR-corrected ACPR rate will be calculated and plotted using the Kaplan-Meier method for each treatment group in the FAS (see [Section 9.4.4](#)).

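### Supportive FAS analysis: a patient switched to another antimalarial for the enrolled infection without ETF, LCF or LPF and film-negative at Day 29 counts as a PCR-corrected responder, and no PCR-corrected analysis scores the switch as non-response

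*SAP*

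**What the plan says.** **Protocol, analysis.** Section 9.4.4 handles antimalarials in the FAS by reason for use. Patients given rescue for *P. falciparum* malaria ("except for the treatment of a new infection) will be considered treatment failures (from the day of rescue use onwards") are failures. A separate group, "Patients who received other concomitant medication having an effect on malaria for reasons other than rescue therapy", is analysed without regard to the drug; the examples are treatment of *P. vivax* and of gametocytes. Section 9.5.1.1 repeats both rules for the secondary ACPR analyses. For Kaplan-Meier, 9.4.4 censors at first use of antimalarial "medications for reinfection or reasons other than rescue medication given for signs and symptoms of infection with" *P. falciparum* or for unsatisfactory effect.

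**Protocol, use of the term rescue.** Section 5.6.6 opens with "The following circumstances warrant discontinuation of study treatment and the implementation of rescue medication" and lists ETF, LCF and LPF. Section 5.7.2 allows rescue, at the investigator's discretion, after any of its listed reasons for discontinuation. These include adverse events, laboratory values and a vomited replacement dose. Section 5.6.4 calls the treatment after a vomited replacement dose standard of care.

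**SAP.** Section 2.4.2 counts an antimalarial as rescue when it follows discontinuation for ETF, LCF or LPF; "otherwise, they are considered as other non-study drug antimalarial medications". The same section adds: "Rescue medications will be captured along with other concomitant medications by the investigators under rescue medication category". Section 2.5.4 then says of the FAS: "Patients who received non-rescue anti-malarial medication will be considered in the analysis as if they had not taken the anti-malarial drug". Section 2.1.1.2 defines ACPR from blood film and PCR alone. Section 4 declares no change from the protocol.

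**The concern.** The FAS analysis brings back the patients whom the PPS leaves out. If some of them were cleared by another drug given for the infection under study, their negative Day 29 film says little about KAF156/LUM-SDF. The FAS rule counts a missing Day 29 film as non-response, unless a later film is negative, but counts a film-negative switch as response. Several routes to a switch are matters of tolerability, such as vomiting or an adverse event, so their frequency could differ between regimens.

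The protocol and SAP can also score the same patient differently. If the use is called rescue, as in protocol 5.7.2, protocol 9.4.4 makes the patient a failure. Under SAP 2.4.2 and 2.5.4 the patient is a responder.

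The group is narrow. Unsatisfactory therapeutic effect in protocol 5.7.2 refers to the failure criteria of 6.5.8, so most switches for lack of effect are already formal failures.

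**Working it through.** **1. One patient through each PCR-corrected analysis.** Take an FAS patient who vomits the replacement dose on Day 1, receives another antimalarial, has no ETF, LCF or LPF, and is film-negative at Day 29.

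| Analysis | Handling of this patient |
|---|---|
| Primary, PPS (SAP 2.2, Table 5-10) | excluded |
| New-infection sensitivity analyses (SAP 2.5.4) | PPS only, so excluded |
| Supportive FAS (SAP 2.5.4) | drug ignored: responder |
| FAS ACPR at Days 15, 29 and 43 (SAP 2.7.2.1) | drug ignored: responder |
| Kaplan-Meier, PCR-corrected (SAP 2.5.4.1) | read literally, event-free to the last film |

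For Kaplan-Meier, SAP 2.5.4.1 censors at non-rescue drug use for other infections. This patient's drug was for the enrolled infection, so the remaining rule (censor at last parasite assessment) applies. Protocol 9.4.4 and SAP 2.5.4.2 (uncorrected ACPR) are both broader.

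The one analysis that scores the switch as non-response is the FAS sensitivity analysis in SAP 2.7.2.2, for uncorrected ACPR at Day 29.

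**2. Why SAP 2.7.2.2 bounds the effect only loosely.** It also rescores drugs given for other species or gametocytes (primaquine is in Table 5-8) and PROH01b drugs, so it can overstate. It can also understate. A switched patient with a later PCR-confirmed new infection is already an uncorrected non-responder, yet SAP 2.7.2.1 keeps that patient as a PCR-corrected responder. Example: of two switchers, one film-negative and one with a later new infection, 2.7.2.2 lowers the uncorrected count by 1, whereas the PCR-corrected count would fall by 2.

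**3. The plan's design figures.** With the smallest count whose Clopper-Pearson lower limit exceeds 0.80, exact power at a true rate of 95% is 85.3% at n = 41 (38 responders) and 84.3% at n = 42 (39 responders). Both agree with the stated power of about 80% or higher. The inflation 42/(1 − 0.16) = 50 also reproduces.

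**4. Sensitivity at n = 50.** Assume all 50 randomized patients in a KAF156/LUM-SDF arm enter the FAS. Exact lower limits:

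| Responders of 50 | Lower limit |
|---|---|
| 42 | 0.7089 |
| 44 | 0.7569 |
| 45 | 0.7819 |
| 46 | 0.8077 |
| 47 | 0.8345 |

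So 46 responders are needed. Each rescored patient moves the rate by 1/50 = 2.0 points (1/25 = 4.0 points in the Coartem arm). With o other non-responders and s film-negative switchers, the result changes only if o ≤ 4 and o + s ≥ 5:

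| o | smallest s that changes the result |
|---|---|
| 4 | 1 |
| 3 | 2 |
| 2 | 3 |
| 1 | 4 |
| 0 | 5 |

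With o ≥ 5 the lower limit is below 80% under either rule.

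**5. At the planned 16% exclusions.** Let 8 of 50 be excluded from the PPS: s film-negative switchers and 8 − s with missing films. Let f of the other 42 fail.
- As written: responders = 42 − f + s. Reaching 46 needs s ≥ 4 + f.
- Switch scored as non-response: responders = 42 − f, at most 42, lower limit at most 0.7089.

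The result can therefore change only if s ≥ 4 + f. At the design rate of 95%, expected f = 42 × 0.05 = 2.1, and the chance of f = 0 is 0.95^42 = 11.6%. With f = 2, six of the eight would have to be switchers.

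**6. Kaplan-Meier illustration.** For 50 patients with 2 switchers on Day 2 and 3 later failures among the other 48: 47/50 = 94.0% if the switchers stay event-free, 45/48 = 93.8% if censored at the switch, 45/50 = 90.0% if counted as events.

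**The case against.** The strongest reply is that this is a defensible choice in a study declared exploratory. The FAS follows the intent-to-treat principle, protocol 9.4.4 itself ignores non-rescue antimalarials, non-study antimalarial use is tabulated and listed (SAP Table 2-6), and SAP 2.7.2.2 already gives a non-response version on the FAS. Much of this stands and keeps the point small. It does not close the gap: the protocol's examples of drugs to ignore are for *P. vivax* and gametocytes, not replacement treatment of the enrolled infection, and 2.7.2.2 is for a different endpoint.

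It can also be said that the SAP largely settles the classification. SAP 2.4.2 says which uses are rescue, and the note in 2.5.4 ties the non-rescue rule to patients without treatment failure. That is fair. What remains is that the SAP's definition is narrower than the term in protocol 5.7.2, and this is not declared. The sentence in protocol 5.6.6 leaving rescue to the investigator's judgment is weak evidence of conflict, since it can be read as setting only the timing for the listed failures.

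The Kaplan-Meier reading is likely but not certain. SAP 2.5.4.1 gives *P. falciparum* gametocytes as its example of another infection, so the wording is loose, and the SAP says that it follows section 9 of the protocol. Censoring would move the illustration by only 0.2 points.

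A reader might infer that the primary result is inflated. The documents do not support that: the formal test uses the PPS, and Table 5-10 excludes this patient. Nor do they support the inference that one switch would typically decide the FAS result; step 5 shows how much more is needed at the planned exclusion rate.

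**Conclusion.** The point holds and is minor. Under SAP 2.4.2 and 2.5.4, a film-negative patient switched for the enrolled infection without ETF, LCF or LPF is a PCR-corrected FAS responder, and no PCR-corrected analysis shows the result with the switch scored as non-response. The SAP's narrower definition of rescue, and its narrower censoring wording in 2.5.4.1, depart from protocol 9.4.4 as read with 5.7.2, while SAP section 4 declares no change. The formal 80% test is not affected.

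The size cannot be estimated, because the documents give no switch rate. The figures above are illustrations for a single arm. They assume that all 50 randomized patients enter the FAS; step 5 also assumes that PPS exclusions are only missing films or film-negative switchers. Under those assumptions the FAS conclusion depends on the rule only when s ≥ 4 + f.

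**What to change.** 1. Add one FAS sensitivity row per arm for PCR-corrected ACPR at Day 29. Score as non-responder any patient who, before Day 29 and before any ETF, LCF or LPF, took a non-study antimalarial as treatment for the enrolled *P. falciparum* infection, including one with a later new infection. Leave out drugs given for other species or gametocytes and PROH01b drugs, or show them in a separate row. Copying SAP 2.7.2.2 unchanged would carry those drugs along and would not isolate the switches.
2. In SAP 2.5.4.1, censor at first use of any non-rescue antimalarial, as SAP 2.5.4.2 and protocol 9.4.4 do.
3. Declare in SAP section 4 that the SAP's definition of rescue is narrower than the protocol's use of the term. Note that protocol 5.6.4, 5.6.6 and 5.7.2 must be reconciled on that term. This concerns scoring only, not which treatment a patient should receive.

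The cost is one row per arm, one censoring rule and one declaration, using concomitant-medication data already collected. Changing the protocol wording itself would need an amendment. The SAP's revision log already has an entry after final database lock, so an analysis added after lock should be labelled post hoc.

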2.5.4.1 Analysis of PCR-corrected ACPR rate using Kaplan-Meier method

For the FAS, the proportion of patients with PCR-corrected ACPR at Day 29 and 95% CI will be also estimated using the Kaplan-Meier method ([Stepniewska and White 2006](#) and [WHO 2015](#))

Event = PCR-corrected non-responder during the study (same as at Day 15, Day 43, See Section 2.1). The event time is the first time when the patient becomes a non-responder based on PCR-correction. If a patient parasite is not cleared at all, Day 7 is considered as the event time.

The PCR-corrected responder rate at Day 29 is estimated by the survivor function at Day 29 using the Kaplan-Meier method.

Rule for censoring:

The following censoring rules will be applied to the patients who were not non-responder

- Patients who had a new infection (i.e., reinfection) with *P. falciparum* or other species without *P. falciparum* recrudescence on or after Day 8 will be censored at the first time of the PCR that indicate the infection or blood smear with other species;
- Patients who received non-rescue antimalaria medication for other infections, such as *P. falciparum* gametocytes, will be censored at the first time of antimalaria medication;
- Patients who have parasites at Day 8 or later but cannot be determined as recrudescence or new infection due to missing PCR genotyping will be censored at the time of the first malaria blood film with presence of parasites on or after Day 8.
- other patients not classified as non-responder will be censored at the time of last parasitemia assessment.

A two-sided 95% CI for the difference in proportion of responders between each KAF156/LUM-SDF combination treatment group and Coartem[®] will be calculated based on the variance of individual proportion using the Greenwood formula.

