## 1.2 Purpose

This Phase 2 study aims to determine the most effective and tolerable dose at the shortest dosing regimen of the investigational drug KAF156 and a Solid Dispersion Formulation of lumefantrine (LUM-SDF) in combination in adult/adolescent and pediatric patients with uncomplicated *P. falciparum* malaria. Different dose combinations and dosing regimens (i.e., 3-, 2-, and 1-day regimens) of KAF156 and LUM-SDF in combination and a reference product Coartem® will be assessed.

This study is set up in a three-part sequential design. Following the PK Run-in Part, Part A of the study will determine in adults and adolescents (greater than or equal to 12 years of age and with a body weight  $\geq 35.0$  kg) the most effective and tolerated dose regimens to be carried forward into Part B which will be conducted in pediatric (2 to < 12 years old and with a body weight  $\geq 10.0$  kg) population. Combined data obtained from Parts A and B will then form the basis for identifying the dose regimen(s) that should be further investigated in Phase 3 development in adults and children down to 2 years of age.

Coartem® will be used as a control for trial sensitivity in Parts A and B so as to evaluate if any significant safety issues or low efficacy results observed in the experimental treatment groups for both adults/adolescents and children are due to treatment or population. It will also provide preliminary relative efficacy for experimental treatment groups compared to the control although it's not statistically powered to show non-inferiority or superiority.

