Note - The outcome of PCR-corrected ACPR and uncorrected ACPR at a given day is categorized as responder or non-responder to distinguish from failure used in early treatment

failure, late clinical failure or late parasitological failure. With this notation, ACPR rate is the proportion of responders.

Recurrence of parasitemia after 7 days is considered as non-responder for uncorrected ACPR. We reclassify such patient as responder for PCR-corrected ACPR if recurrence of parasitemia after 7 days is due to new infection. Whether the recurrence of parasitemia after 7 days is due to recrudescence or new infection is determined and provided by the central laboratory. Negative PCR will categorize the patient as PCR corrected responder.

The above definitions of ACPRs are purely based on the malaria blood film and PCR results without consideration for taking concomitant anti-malaria drugs. In statistical analyses, some responses may be overridden for patients who take concomitant anti-malaria drugs (see [Sections 2.5 and 2.7](#)).

Fever Clearance is defined (in patients with axillary temperature of $\geq 37.5^{\circ}\text{C}$ at baseline) as the time of the first measurement of at least 2 consecutive axillary temperatures of $< 37.5^{\circ}\text{C}$ (or $< 38.0^{\circ}\text{C}$ for alternative routes) measured at least 24 hours apart.

Time to parasite clearance (PCT) is defined as time from the first dose until the first total and continued disappearance of asexual parasite forms which remained at least a further 48 hours

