2.5.4.2 Analysis of uncorrected ACPR rate using Kaplan-Meier method

For the FAS, the proportion of patients with uncorrected ACPR at Day 29 and 95% CI will be also estimated using the Kaplan-Meier method ([Stepniewska and White 2006](#) and [WHO 2015](#))

Event = PCR-uncorrected non-responder during the study (same as at Day 15, Day 43, See [Section 2.1](#)). The event time is the first time when the patient becomes a non-responder without PCR-correction. If a patient parasite is not cleared at all, Day 7 is considered as the event time.

The uncorrected ACPR rate at Day 29 is estimated by the survivor function at Day 29.

Rule for censoring:

The following censoring rules will be applied to the patients who were not non-responders

- Patients who cleared the initial infection by Day 7 and are re-infected with species different than *P. Falciparum* will be censored at the time of re-infection.
- Patients who received non-rescue anti-malaria medication will be censored at the first time of anti-malaria medication;
- other patients will be censored at the time of last parasitemia assessment.

An asymptotic two-sided 95% CI for the difference in proportion of responders between each KAF156/LUM-SDF combination treatment group and Coartem[®] will be calculated from the z-test statistic distribution based on the variance of individual proportion using the Greenwood formula.

The confidence interval will be constructed as: $(r_k - r_c) \pm Z_{\alpha/2} * SE_d$,

where,

I_T = Kaplan-Meier estimate for the investigational group at time t,

I_C = Kaplan-Meier estimate for the control group at time t,

$SE_d = \sqrt{(SE_k^2 + SE_c^2)}$,

SE_T = estimated standard error for the investigational group based on Greenwood's formula,

SE_C = estimated standard error for the control group based on Greenwood's formula,

$Z_{\alpha/2}$ = z-statistic = $\text{probit}(1 - \alpha/2)$ from a normal distribution function,

$\alpha = 0.05$.

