2.7.2.1 PCR-corrected ACPR and uncorrected ACPR

At each visit, the ACPR rate with 95% confidence intervals will be provided using Pearson-Clopper method for each treatment group.

Handling of missing values/censoring/discontinuations

Data will be handled as follows for ACPRs (PCR corrected or uncorrected):

- Presence of parasitemia which were determined to be reinfection on Day 8 or later will be counted as responders for PCR corrected ACPR and as non-responder for PCR uncorrected ACPR from the day of test
- Presence of parasitemia which cannot be determined to be recrudescence or reinfection due to missing PCR data will be counted as non-responders from the day of test
- Missing/underdetermined responses at a visit due to missing blood smear data at the visit will be counted as non-responders (PCR corrected or uncorrected) unless there is a later blood smear test indicating no parasitemia
- Patients who received non rescue anti-malarial medication will be considered in the analysis as if they had not taken the antmalarial drug

In addition, PCR-corrected and uncorrected ACPR rate will be calculated and plotted using the Kaplan-Meier method for each treatment group in the FAS (see [Section 2.5.4](#)).

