5.6.3 Other secondary XXXXXXXXXX analysis

Kaplan-Meier estimates

An estimate of the survival function in each treatment group will be constructed using Kaplan-Meier (product-limit) method as implemented in PROC LIFETEST with METHOD=KM option. The PROC LIFETEST statement will use the option CONFTYPE=LOGLOG.

Median survival for each treatment group will be obtained along with 95% confidence intervals calculated from PROC LIFETEST output using the method of [[Brookmeyer and Crowley 1982](#)]. Kaplan-Meier estimates of the survivor function with 95% confidence intervals at specific time points will be summarized. The standard error of the Kaplan-Meier estimate will be calculated using Greenwood’s formula [[Collett 1994](#)].

Difference in responder rates stratified by part using Mantel-Hanszel estimate

For PCR corrected and uncorrected ACPR rates, the treatment differences versus control will be evaluated using a Mantel-Haenszel estimate of the treatment difference in responder rates stratified by Part using PROC FREQ with RISKDIFF(COMMON) option in the TABLES statement).

Difference in responder rates using the Wilson uncorrected method

For PCR corrected and uncorrected ACPR rates, the treatment differences versus control will be evaluated using a Wilson uncorrected method using PROC FREQ with RISKDIFF (CL=WILSON) option in the TABLES statement.

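### The Kaplan-Meier difference interval against Coartem gives an arm with no failures zero variance, and the SAP has no rule for that case

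*SAP*

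**What the plan says.** SAP 2.5.4.1 estimates PCR-corrected ACPR in the FAS by the Kaplan-Meier survivor function at Day 29. The two-sided 95% interval for the difference between each KAF156/LUM-SDF group and Coartem "will be calculated based on the variance of individual proportion using the Greenwood formula". Protocol 9.4.4 has the same rule. SAP 2.5.4.2 repeats it for uncorrected ACPR, where the interval "will be calculated from the z-test statistic distribution based on the variance of individual proportion using the Greenwood formula", and writes it out as the difference plus or minus z times the root of the summed squared standard errors.

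For the curve in each arm, SAP 5.6.3 states: "The PROC LIFETEST statement will use the option CONFTYPE=LOGLOG".

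Two other FAS intervals are planned. In SAP 2.5.4 the interval for the Day 29 difference in ACPR "will be constructed using the Wilson uncorrected method"; SAP 5.6.3 names that method for both corrected and uncorrected ACPR. SAP 2.7.2.1 adds: "At each visit, the ACPR rate with 95% confidence intervals will be provided using Pearson-Clopper method for each treatment group". These binary analyses count missing outcomes as non-response, whereas the Kaplan-Meier analysis censors them.

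None of these sections says what to do, or which interval to read, when an arm has no failures.

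**The concern.** The Kaplan-Meier analysis is the FAS check that censors missing data instead of counting it as failure. Its difference interval should therefore be usable in the outcomes the trial is likely to produce. A small control arm with a high cure rate can easily have no failures, and the specified formula then treats the Coartem rate as known without error. The interval becomes too narrow and can lie wholly below zero on data that the planned Wilson interval regards as compatible with no difference. The single-arm limits offer no way out: the log-log transform needs log(-log S), which is undefined at S = 1.

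**Working it through.** **Plan figures.** The documents give no figure for this interval. Their arm sizes reproduce: 42/0.84 = 50 per experimental arm, 21/0.84 = 25 for Coartem, and 6 x 50 + 25 = 325. I use 50 v 25 as the planned sizes.

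**Formula.** Greenwood: Var S(t) = S(t)^2 x sum of d/[n(n-d)] over event times. With no events every d is 0, so the variance is 0 whatever the censoring. Without censoring it reduces to S(1-S)/n.

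**Chance of no failures in Coartem (n = 25).** True rates of 95-98% are an assumption.
- 0.95^25 = 0.277
- 0.97^25 = 0.467
- 0.98^25 = 0.603

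**Examples against Coartem 25/25, no censoring (points).**

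| Experimental | Greenwood | Wilson (SAP 2.5.4) |
|---|---|---|
| 50/50 | 0.0 to 0.0 | -7.1 to +13.3 |
| 49/50 | -5.9 to +1.9 | -10.5 to +11.4 |
| 47/50 | -12.6 to +0.6 | -16.2 to +7.9 |
| 46/50 | -15.5 to -0.5 | -18.8 to +6.2 |
| 43/50 | -23.6 to -4.4 | -26.2 to +1.1 |
| 42/50 | -26.2 to -5.8 | -28.5 to -0.6 |

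For 46/50: SE = sqrt(0.92 x 0.08/50) = 0.0384, and -8.0 +/- 1.96 x 3.84 gives -15.5 to -0.5. Greenwood excludes zero from 46/50 downwards and Wilson only from 42/50. The exact single-arm interval for 25/25 is 86.3% to 100%.

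**Coverage.** Exact enumeration over Binomial(50, p1) x Binomial(25, p2), no censoring, experimental v Coartem:

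| True rates (%) | Greenwood | Wilson |
|---|---|---|
| 95 v 95 | 92.9% | 98.0% |
| 95 v 97 | 94.2% | 97.7% |
| 95 v 98 | 93.9% | 99.0% |
| 97 v 95 | 72.0% | 99.0% |
| 97 v 97 | 96.9% | 98.9% |
| 97 v 98 | 85.5% | 99.7% |
| 98 v 95 | 71.9% | 98.5% |
| 98 v 97 | 79.1% | 98.4% |
| 98 v 98 | 98.9% | 99.5% |

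The 72% has a simple source. Against 25/25 without censoring, the largest Greenwood upper limit is +1.9 points (at 49/50). A true advantage of 2 or 3 points is then missed whenever Coartem has no failures, so coverage cannot exceed 1 - 0.277 = 72.3%.

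**With censoring.** Take one failure among n at risk in the experimental arm and none in Coartem. The difference is -1/n and SE = (1 - 1/n)/sqrt(n(n-1)). The upper limit is +2.04 points at n = 46, +2.08 at 45 and +2.23 at 42.

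**Uncorrected analysis (2.5.4.2).** The SAP says: "Recurrence of parasitemia after 7 days is considered as non-responder for uncorrected ACPR". New infections are therefore events, and an arm with no failures is much less likely. At assumed uncorrected success of 80%, 85% and 90%, the chance of none among 25 is 0.4%, 1.7% and 7.2%. At 85 v 85, coverage is 92.9% for Greenwood and 95.7% for Wilson.

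**The case against.** The best defence is that little depends on this interval. Cohort success rests on the exact single-arm lower limit in the PPS. Protocol 1.2 calls the Coartem comparison "not statistically powered to show non-inferiority or superiority", and the SAP labels the Day 29 difference exploratory. A (0, 0) interval would be reported alongside a Wilson interval of -7.1 to +13.3. All of that stands and sets the priority, but it does not make the formula valid, and the SAP does not tell the reader which interval to use.

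Some stronger readings are tempting and are not supported.
- A reader might infer that a 2-point advantage can never be covered once Coartem has no failures. That holds only without censoring. This analysis does censor, and the upper limit can then reach about +2.0 to +2.2 points.
- A reader might quote 76.0% coverage, or zero excluded in 24% of cases, at equal 95% rates. Both are conditional on observing Coartem 25/25; overall coverage there is 92.9%.
- A reader might conclude that Wilson is better throughout. At 95 v 95 its 98.0% is further from the nominal 95% than Greenwood's 92.9%. Its gain comes when an arm has no failures or when the true rates differ.
- A reader might infer that the curve read at Day 29 drops failures first found on Days 30-33. SAP 2.5.3 assigns assessments from Days 25-33 to Day 29 for this same endpoint and does not exclude the Kaplan-Meier analysis, so its rule can reasonably be carried over. Saying so would be a clarification; its absence is not a defect.

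**Conclusion.** The point holds, as a minor one confined to the supportive FAS Kaplan-Meier analyses: mainly SAP 2.5.4.1 and Protocol 9.4.4, and less so SAP 2.5.4.2. The zero variance is a property of the formula and needs no assumption. How often it matters does: at an assumed Coartem rate of 95-98% the chance of a failure-free control arm is 28-60%. Without censoring, overall coverage is close to nominal at equal 95% rates and about 72% when the experimental arm is truly 2-3 points better than a 95% control. The harm is false precision in an exploratory contrast. The primary test, the success rule and the sample size do not change.

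**What to change.** Add one sentence to SAP 2.5.4.1 and 2.5.4.2: when either arm has no failures by Day 29, the Greenwood difference interval and the log-log single-arm limits are not interpreted, and the Wilson difference interval and exact single-arm interval already planned for the FAS are used instead, noting that these count missing outcomes as non-response.

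Record it in SAP section 4, which now lists no changes, as a departure from Protocol 9.4.4, where Greenwood is specified. Date the entry, because the SAP's change log includes updates made after final database lock and a rule adopted then would be post hoc.

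The cost is wording only; both replacement intervals are already programmed under the plan. The price is that, in this case, the interval comes from an analysis that counts missing data as failure instead of censoring it.

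An optional alternative keeps the censoring: apply the square-and-add Wilson formula of SAP 2.5.4 to the Kaplan-Meier estimates. The effective sample size in each arm would be S(1-S)/Greenwood variance when S < 1 and the number at risk at Day 29 when S = 1. This needs a new rule and minor programming, and it is conservative (about 98% coverage at 95 v 95), so it is a matter of choice.
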